#### **5.4.2.2 Symptoms evaluation**

##### **a) Objective 3:**

To estimate the margin and variance of prophylactic effect of IV treatment with Palivizumab administered 1 day prior to inoculation in the RSV human challenge model in healthy adults compared to Placebo [assessed by total symptom score (TSS)].

A total symptom score will be derived for each subject, separately for each assessment (symptom diary card) on each day, as the sum of the 13 observed symptom grade values for each symptom diary card to obtain a total symptom score for each symptom diary card. If the subject does not have all 13 observed values on a specific symptom diary card being considered, then total symptom score will not be calculated for that symptom diary card. It is expected that subjects will not have missing data.

 Venn Life Sciences <small>Think Research</small>	Document Number or Project Identification: VH0001 / MB05-P-01-20
	Document Version: v3
Statistical Analysis Plan	

Area under the total symptom score-time curve (TSS-AUC) collected daily in the participant symptom diary card starting one day post-viral challenge (Day +1) up to the end of quarantine will be calculated (using the trapezium rule) and tabulated per treatment group. Treatment groups will be compared using t-test if assumptions are valid (Statistical Table 14.2.5.1). In case of distribution not normal, a data transformation could be used.

The TSS will be also tabulated per visit/timepoint for each treatment group (Statistical Table 14.2.5.2). Spaghetti plots and mean value over time will be used for graphical presentation of TSS, boxplot will be used for AUC presentation (Statistical Figures 14.1.4.1 to 14.1.4.3).

Following tables will also be displayed:

- Qualitative description for each symptom per visit/timepoint and treatment group (Statistical Table 14.2.5.3)
- Quantitative description (in mm) for each symptom per visit/timepoint and treatment group (Statistical Table 14.2.5.4)

Individual data for Symptom diary cards (included data) will be presented on Listing 16.2.6.3.

**b) Objective 4:**

To estimate the margin and variance of prophylactic effect of IV treatment with Palivizumab administered 1 day prior to inoculation in the RSV human challenge model in healthy adults compared to Placebo [assessed by total symptom score (TSS)].

Sum Total symptom score-time curve (TSS-Sum) collected daily in the participant symptom diary card starting one day post-viral challenge (Day +1) up to the end of quarantine will be analysed using a MMRM if underlying assumptions valid (Statistical Table 14.2.5.5).

**c) Objective 7**

Peak symptom score defined by the maximum daily sum of Symptom score starting one day post viral challenge (Day +1) up to the end of quarantine will be determined and tabulated per treatment group. Treatment groups will be compared using t-test if assumptions are valid (Statistical Table 14.2.6.1). In case of distribution not normal, a data transformation could be used.

Peak symptom score will be also described graphically using boxplot (Statistical Figure 14.2.4.4).

Number of days with symptoms of grade 2 or more, starting one day post viral challenge (Day +1) up to the end of quarantine will be calculated and tabulated per treatment group. Treatment groups will be compared using t-test if assumptions are valid (Statistical Table 14.2.6.2). In case of distribution not normal, a data transformation could be used. In case of missing data on at least one visit, the number of days will be considered as missing for the subject, except if grade 2 or more is already recorded on other timepoint for this visit.

**5.4.2.3 Weight of mucus produced**

**a) Objective 5:**

To estimate the margin and variance of prophylactic effect of IV treatment with Palivizumab administered 1 day prior to inoculation in the RSV human challenge model in healthy adults compared

 Venn Life Sciences <small>Think Research</small>	Document Number or Project Identification: VH0001 / MB05-P-01-20
	Document Version: v3
Statistical Analysis Plan	

to Placebo [assessed by total weight of nasal discharge produced and the total number of tissues used in each group].

Total weight of nasal discharge produced and total number of tissues used by participants starting one day post viral challenge (Day +1) up to the end of quarantine will be calculated and tabulated per treatment group. Treatment groups will be compared using t-test if assumptions are valid (Statistical Table 14.2.7.1). In case of distribution not normal, a data transformation could be used.

In addition, weight of nasal discharge produced and number of tissues used by participants will be also tabulated per visit for each treatment group (Statistical Tables 14.2.7.2 and 14.2.7.3 respectively).

Individual data for 24-hour tissue count and nasal discharge weight (included derived data) and will be presented on Listing 16.2.6.4.

#### **5.4.2.4 Incidence of infection & illness**

##### **a) Objective 6:**

To estimate the margin and variance of prophylactic effect of IV treatment with Palivizumab administered 1 day prior to inoculation in the RSV human challenge model in healthy adults compared to Placebo [assessed by viral shedding of RSV-A Memphis 37b in nasal samples, in terms of incidence, duration, and peak].

Incidence of laboratory-confirmed infection (variant 1) and incidence of laboratory-confirmed infection (variant 2) will be presented by treatment group and compared using chi-square test (Statistical Tables 14.2.8.1 and 14.2.8.2).

##### **b) Objective 7:**

To estimate the margin and variance of prophylactic effect of IV treatment with Palivizumab administered 1 day prior to inoculation in the RSV human challenge model in healthy adults compared to Placebo [assessed by symptomatic infection in terms of incidence, duration, and peak].

Incidence of laboratory-confirmed virus-like-illness (Variant 3) will be presented. Treatment group will be compared using chi-square test on both the composite and each component (Statistical Table 14.2.9).

The following infections and illness will be summarised in one Table including data per subject and description by treatment group (Statistical Tables 14.2.10):

- “Laboratory-confirmed infection” (variant 1)
- “Laboratory-confirmed virus-like-illness” (variant 1)
- “Laboratory-confirmed virus-like-illness” (variant 2)
- Upper respiratory tract illness (URTI)
- Lower respiratory tract illness (LRTI)
- Systemic illness (SI)
- Febrile Illness (FI)
- Fold seroconversion

All Infections data will also be presented in Listing 16.2.6.5.

 Venn Life Sciences <small>Think Research</small>	Document Number or Project Identification: VH0001 / MB05-P-01-20
	Document Version: v3
Statistical Analysis Plan	

In addition, the following proportions will be tabulated per treatment group:

- Proportion of Subjects with Grade 2 or higher symptoms on any occasion at any time (Statistical Table 14.2.11.1)
- Proportion of Subjects with Grade 2 or higher Symptoms on any occasion for each day separately (Statistical Table 14.2.11.2)
- Proportion of Subjects with Grade 2 or higher Symptoms on two separate occasions at any time (Statistical Table 14.2.11.3)
- Proportion of Subjects with Grade 2 or higher Symptoms on two separate occasions for each day separately (Statistical Table 14.2.11.4)
- Proportion of Subjects with any symptom (grade  $\geq 1$ ) on any occasion at any time (Statistical Table 14.2.11.5)
- Proportion of Subjects with any symptom (grade  $\geq 1$ ) on any occasion for each day separately (Statistical Table 14.2.11.6)
- Proportion of Subjects with any symptom (grade  $\geq 1$ ) on two separate occasions at any time (Statistical Table 14.2.11.7)
- Proportion of Subjects with any symptom (grade  $\geq 1$ ) on two separate occasions for each day separately (Statistical Table 14.2.11.8)

#### 5.4.2.5 Temperature

The highest tympanic temperature will be calculated and tabulated per treatment group (Statistical Table 14.2.12)

#### 5.4.3 Tertiary/Exploratory efficacy analyses

Tertiary and exploratory objectives are optional and are not included in the list of Tables of this SAP. They might be performed as additional analyses depending on the results of the study.

##### a) **Objective 12:**

To explore the Minimal Clinically Important Difference (MCID) in instrument change

The average amount of instrument-assessed change for all participants who rate themselves as "a little better" or "somewhat better" may be presented per treatment group.

##### b) **Objective 13:**

To explore the margin and variance of prophylactic effect of IV treatment with Palivizumab administered 1 day prior to inoculation in the RSV human challenge model in healthy adults compared to Placebo in relation to baseline immune status.

The above endpoints may be explored in relation to the baseline status of volunteers and the response to treatment. Baseline status and response can be regarding, but not limited to:

- Immune assays related to Palivizumab (e.g. IgG anti-F ELISA, PCA)
- Baseline immunity to RSV
- Response to Palivizumab treatment

##### c) **Objective 14:**

To explore the host-pathogen relationship in the RSV human challenge model in healthy adults .

 Venn Life Sciences <small>Think Research</small>	Document Number or Project Identification: VH0001 / MB05-P-01-20
	Document Version: v3
Statistical Analysis Plan	

## 5.5 Pharmacokinetic (PK) analyses

### **Objective 1:**

To assess the pharmacokinetics of Palivizumab in the RSV human challenge model in healthy adults.

Pharmacokinetic analysis will be described in a separate Clinical Pharmacology analysis plan. Date and time of pharmacokinetic sample will be provided on Listing 16.2.6.6.

## 5.6 Safety analyses

Safety variables will be tabulated and presented for all subjects included in the SAF population.

### 5.6.1 Extent of exposure and compliance

IMP/Placebo dosing and Challenge virus inoculation information will be presented respectively in Listings 16.2.5.1 and 16.2.5.2). Compliance, defined as proportion of prescribed study drug actually taken (see section 10) will also be presented in Statistical Table 14.3.9 on evaluable and SAF populations.

### 5.6.2 Adverse events

**Objective 8:** To assess safety of Palivizumab in the RSV human challenge model in healthy adults.

#### **Adverse event tabulations:**

Tabulation of adverse events will present for each cell the following information: number of subjects with at least one occurrence of the event, corresponding percentage and number of events.

The following tables will be produced by treatment group:

- Summary table of adverse events (Statistical Table 14.3.1.1):
  - Any AE
  - Any TEAE
  - Any TEAE leading to study discontinuation
  - Any TEAE considered related to the study treatment (at least possibly related)
  - Any SAE
  - Any SAE leading to study discontinuation
  - Any SAE considered related to the study treatment
  - Death (if any)
  
- Detailed Tables:
  - TEAEs by SOC and PT (Statistical Table 14.3.1.2)
  - TEAEs by SOC, PT and severity (Statistical Table 14.3.1.3)
  - At least possibly related TEAEs by SOC, PT and severity (Statistical Table 14.3.1.4)
  - Listing of deaths (Statistical Table 14.3.2)
  - Narrative of deaths, other serious and significant adverse events (Statistical Table 14.3.3)

#### **Adverse event listings:**

 Venn Life Sciences <small>Think Research</small>	Document Number or Project Identification: VH0001 / MB05-P-01-20
	Document Version: v3
Statistical Analysis Plan	

A by-patient AE data listing including onset and resolution dates, verbatim term, preferred term, blinded treatment, severity, relationship to treatment, action taken, and outcome will be provided in Listing 16.2.7.

### 5.6.3 Laboratory safety variables

The laboratory values will be directly transferred to the data management department. The laboratory report was interpreted by the investigator. Any clinically relevant changes occurring during the trial were recorded on the AE Form of the CRF.

Laboratory evaluations will be summarized by visit and by treatment group on the SAF population (Statistical tables 14.3.4.1 to 14.3.4.12).

For each hematology, chemistry, coagulation and cardiac enzymes variables:

- Quantitative descriptive statistics will be tabulated at each time over the course of the study (e.g., at each visit) on raw values and change from baseline
- Qualitative descriptive statistics will be tabulated for each laboratory variable at each time over the course of the study by clinical significance (normal, abnormal NCS, abnormal CS) (if relevant)

All urinalysis parameters will also be analyzed as qualitative or quantitative variables per visit (Statistical table 14.3.4.13).

All laboratory results will be presented in Listings 16.2.8.

The following listings will be presented:

- Laboratory reference ranges
- Hematology
- Biochemistry
- Coagulation
- Cardiac enzymes
- Urinalysis

### 5.6.4 12-Lead Electrocardiogram (ECG)

Quantitative descriptive statistics will be tabulated for each ECG parameters collected [HR (bpm), QRS (ms), PR interval (ms), QT (ms), QTc (ms), QTcF (ms), QTcB (ms), RR (ms)] at each time over the course of the study (e.g., at each visit) on raw values and change from baseline by treatment group. Clinical significance will also be presented for each ECG parameters. (Statistical tables 14.3.5.1 to 14.3.5.3)

In addition, number of patients for the following categories will be displayed for QTcF and QTcB parameters (Statistical Table 14.3.5.4):

- 450 ms
- 480 ms
- 500 ms
  
- < 30 ms increase from baseline
- [30 ms; 60 ms] increase from baseline
- 60 ms increase from baseline

All individual measurements will be provided in Listing 16.2.9.

 Venn Life Sciences <small>Think Research</small>	Document Number or Project Identification: VH0001 / MB05-P-01-20
	Document Version: v3
Statistical Analysis Plan	

### 5.6.5 Physical examinations

Number of normal, abnormal NCS and abnormal CS values will be presented at each visit by body systems for each treatment group to describe complete physical examination (Statistical Table 14.3.6.1).

Direct physical examination will also be presented. Upper respiratory tract (URT) (nasal discharge, otitis, pharyngitis, sinus tenderness) and lower respiratory tract (LRT) (New Wheezes, Rhonchi) symptoms will be tabulated per visit for each treatment group (Statistical Table 14.3.6.2)

All individual measurements for complete and direct physical examination will be provided respectively in Listings 16.2.10.1 and 16.2.10.2.

### 5.6.6 Vital signs

- Quantitative descriptive statistics will be tabulated for each vital sign recorded [Heart rate (HR) (beats per minutes), Respiratory rate (RR) (breaths per minutes), Systolic BP (SBP) and Diastolic BP (DBP) (mmHg), Oxygen saturation (SpO2) (%), Tympanic temperature (°C)] at each time over the course of the study (e.g., at each visit) on raw values and change from baseline by treatment group (Statistical tables 14.3.7.1 to 14.3.7.2)
- Qualitative descriptive statistics will be presented for each vital sign at each time over the course of the study (e.g., at each visit) by treatment group: number of subjects with abnormal values beyond clinically important limits (HR <50 or >100 beats per minutes, RR <10 or > 20 breaths per minutes, SBP <90 or >140 mmHg, DBP <50 or >90 mmHg, SpO2 <95%, Tympanic temperature <35.5 or >37.8°C) (Statistical table 14.3.7.3)

All individual measurements will be provided in Listing 16.2.11.

### 5.6.7 Concomitant medications

Concomitant medications will be presented by ATC code and Preferred Name by treatment group (Statistical table 14.3.10)

Previous and concomitant medications for each subject will be reported in Listings 16.2.16.

### 5.6.8 ADA

**Objective 10:** To assess the Anti-Palivizumab antibody (ADA) in the RSV human challenge model in healthy adults.

Analyses for ADA results will be described in a separate Clinical Pharmacology analysis plan.

Date and time of samples will be provided on Listing 16.2.6.3.

### 5.6.9 Other safety variables

**Objective 11:** To assess lung function in relation to RSV infection.

Spirometry parameters [FEV1 (L), FEV1/FVC (L)], Peak Expiratory Flow (PEF) and Forced Oscillation Technique (FOT) will be presented. Results at each time over the course of the study will be tabulated on raw values and change from baseline by treatment group (Statistical Tables 14.3.8.1 to 14.3.8.6).

Individual data will be provided in Listings 16.2.13 to 16.2.15.

 Venn Life Sciences <small>Think Research</small>	Document Number or Project Identification: VH0001 / MB05-P-01-20
	Document Version: v3
Statistical Analysis Plan	

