m	Study specific consent may occur on the day of admission, providing all required eligibility information has been collected through hVIVO Generic Screening process
n	Optional and may be collected or not as per PI discretion for exploratory research
0	Post-dose ECG
р	Adverse events and concomitant mediations are reviewed throughout the study including pre and post dosing with Palivizumab/Placebo and pre and post inoculation.
q	ADA blood samples are taken pre infusion and at 7,13 and 29 days after infusion. Allowable time windows are described I section 8.19.4.
Notes:	Parenthesis indicates the assessment may be optional, or at the PI's discretion. For all participants TDS assessments will commence on Day 0, the first assessment will be pre-virus challenge. The PI may perform additional safety assessments as required. Where any nasal sampling time points occur together, the order of sampling will typically be (1) Nasopharyngeal swab followed by (2) Nasal wash.

MB05-P-01-20 Protocol Final V2.0

GENOMIC, TRANSCRIPTOMIC AND PROTEOMIC SAMPLES											
DNA/RNA/proteomic sample collection:	Yes		No	$\boxtimes$							
DNA/KNA/proteomic sample collection.	n/a										
Consent considerations:	Future use of remaining sa protocols according to the		oved health research and lal	poratory testing							

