
	Objectives	Endpoints
	Placebo [assessed by symptomatic infection	
 
Incidence of infection, and
 

	in terms of incidence, duration, and peak].	
 
At least one grade 2 symptom from one or more respiratory categories from the participant symptom diary card.
 

		Number of days with symptoms of grade 2 or more, starting one day post-viral challenge (Day +1) up to the end of quarantine.
		Peak symptom score defined by the maximum daily sum of Symptom score starting one day post-viral challenge (Day +1) up to the end of quarantine.
•	To assess safety of Palivizumab in the RSV human challenge model in healthy adults	Frequency and severity of Adverse Events (AEs) and serious AEs (SAEs)
		Frequency and severity of Treatment Emergent Adverse Events (AEs) and serious AEs (SAEs)
		Frequency and severity of drug related Treatment Emergent Adverse Events (AEs) and serious AEs (SAEs)
•	To assess the pharmacokinetics of Palivizumab in the RSV human challenge model in healthy adults	Palivizumab serum concentrations and serum PK parameters through study Day +28
		Nasal concentrations and serum PK parameters through study Day +28
•	To assess the Anti-Palivizumab antibody (ADA) in the RSV human challenge model in healthy adults	Anti-Palivizumab antibody (ADA) through Day 28
	Tertiary/Exploratory	
•	To explore lung function changes in relation to RSV infection	Assessments of spirometry, PEF, and FOT
•	To explore the Minimal Clinically Important Difference (MCID) in instrument change	The average amount of instrument- assessed change for all participants who rate themselves as "a little better" or "somewhat better"
•	To explore the margin and variance of prophylactic effect of IV treatment with Palivizumab administered 1 day prior to inoculation in the RSV human challenge	The above endpoints may be explored in relation to the baseline status of volunteers and the response to treatment. Baseline status and response can be regarding, but not limited to:
	model in healthy adults compared to Placebo in relation to baseline immune status.	Immune assays related to Palivizumab (e.g. lgG anti-F ELISA, PCA)
		Baseline immunity to RSV

Objectives	Endpoints		
Response to Palivizumab treatment			
To explore the host-pathogen relationship in the RSV human challenge model in healthy adults	
 
Immune assays related to Palivizumab
 
RSV baseline immunity and immune responses to infection
 
		

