- Objective 8: To assess safety of Palivizumab in the RSV human challenge model in healthy adults
- Objective 9: To assess the pharmacokinetics of Palivizumab in the RSV human challenge model in healthy adults
- Objective 10: To assess the Anti-Palivizumab antibody (ADA) in the RSV human challenge model in healthy adults
- Objective 11: To assess lung function in relation to RSV Infection (*optional*)
- Objective 12: To explore the Minimal Clinically Important Difference (MCID) in instrument change (*optional*)
- Objective 13: To explore the margin and variance of prophylactic effect of IV treatment with Palivizumab administered 1 day prior to inoculation in the RSV human challenge model in healthy adults compared to Placebo in relation to baseline immune status. (*optional*)
- Objective 14: To explore the host-pathogen relationship in the RSV human challenge model in healthy adults (*optional*)

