#### 3.3.2.3 Safety Analysis Set (SAF)

All participants randomly assigned to study intervention and who take a dose of study intervention, regardless of whether they received the challenge virus or not. Participants will be analysed according to the intervention they actually received.

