## Statistical Analysis Plan

		Enrolled	Evaluable	SAF	Laboratory confirmed infected subgroup
14.3.1.3	TEAEs by SOC, PT and severity			X	
14.3.1.4	At least possibly related TEAEs by SOC, PT and severity			X	
14.3.2	Listing of deaths			X	
14.3.3	Narrative of deaths, other serious and significant adverse events			X	
14.3.4.1	Hematology - Absolute values			X	
14.3.4.2	Hematology - Change from baseline			X	
14.3.4.3	Hematology - Clinical significance			X	
14.3.4.4	Biochemistry - Absolute values			X	
14.3.4.5	Biochemistry - Change from baseline			X	
14.3.4.6	Biochemistry - Clinical significance			X	
14.3.4.7	Coagulation - Absolute values			X	
14.3.4.8	Coagulation - Change from baseline			X	
14.3.4.9	Coagulation - Clinical significance			X	
14.3.4.10	Cardiac enzymes - Absolute values			X	
14.3.4.11	Cardiac enzymes - Change from baseline			X	
14.3.4.12	Cardiac enzymes - Clinical significance			X	
14.3.4.13	Urinalysis			X	
14.3.5.1	12-lead ECG - Absolutes values			X	
14.3.5.2	12-lead ECG - Change from baseline			X	
14.3.5.3	12-lead ECG - Clinical significance			X	
14.3.5.4	12-lead ECG - Abnormalities			X	
14.3.6.1	Complete physical examination			X	
14.3.6.2	Direct physical examination			X	
14.3.7.1	Vital signs - Absolute values			X	
14.3.7.2	Vital signs - Change from baseline			X	
14.3.7.3	Vital signs - Abnormalities			X	
14.3.8.1	Spirometry - Absolute values			X	
14.3.8.2	Spirometry - Change from baseline			X	
14.3.8.3	Peak Exploratory (PEF) - Absolute values			X	
14.3.8.4	Peak Exploratory (PEF) - Change from baseline			X	
14.3.8.5	Forced Oscillation Technique (FOT) - Absolute values			X	
14.3.8.6	Forced Oscillation Technique (FOT) - Change from baseline			X	
14.3.9	Compliance		X	X	
14.3.11	Concomitant medications			X	

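### Optional Objective 11 concerns lung function in relation to RSV infection, but the planned lung-function tables split participants only by treatment arm

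*SAP*

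**What the plan says.** The SAP (2.2.2) lists "Objective 11: To assess lung function in relation to RSV Infection" and marks it optional. Protocol 3.2 has it among the tertiary and exploratory objectives: "To explore lung function changes in relation to RSV infection". The endpoint given there is simply the spirometry, PEF and FOT assessments.

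The analysis is in SAP 5.6.9, under other safety variables: "Results at each time over the course of the study will be tabulated on raw values and change from baseline by treatment group". SAP 5.6 sets the population: "Safety variables will be tabulated and presented for all subjects included in the SAF population". That set takes in everyone dosed, "regardless of whether they received the challenge virus or not" (SAP 3.3.2.3).

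In SAP 11.1 the six lung-function tables run from "Spirometry - Absolute values" (14.3.8.1) to "Forced Oscillation Technique (FOT) - Change from baseline" (14.3.8.6). Each has one mark, under the safety set, and the infected-subgroup column is empty. SAP 6 defines that subgroup by variant 2 of viral shedding and leaves its outputs to the marks in 11.1. SAP 11.2 plans no lung-function figure.

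In the protocol's Part 2 schedule (1.3.2), post-challenge spirometry is in parentheses on Days 1-3, 5-6 and 8-10 and plain on Days 4, 7, 11, 12 and 28. The key reads "Parenthesis indicates the assessment may be optional", or at the investigator's discretion. PEF is plain on every post-challenge quarantine day. FOT is in parentheses throughout.

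**The concern.** The objective names infection as the factor of interest, and the only planned summaries do not use it. A by-arm table describes lung function after palivizumab or placebo. It does not describe lung function in those who became infected against those who did not.

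The plan already has the means. The infected-subgroup mark is on many efficacy tables and on one safety table, the adverse event summary (14.3.1.1). It is absent from the lung-function tables. SAP 5.4.3, which covers the other optional objectives, describes Objectives 12 to 14 and has no entry for Objective 11, so nothing elsewhere fills the gap.

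At stake is a pre-specified answer to one optional objective. If the split is chosen only after unblinding, the infection definition and the handling of partly measured days are chosen with the results in view.

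**Working it through.** **Plan figures used.** Protocol 9.2.2 assumes a 73.7% infection rate. The counts printed beside it, 160 of 216, give 74.1%, a difference that does not matter here. The 25 per arm reproduces: with a 70% reduction of 20.3 (14.21), SD 17.8, two-sided 5% and 80% power, n = 2 × (1.960 + 0.842)² × 17.8² / 14.21² = 24.6, so 25. The documents give no figure for lung function and no expected infection rate under palivizumab.

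**What an arm mean contains.** Let U be the mean change from baseline in uninfected participants, U + D the mean change in infected participants, and p the arm's infection rate. Then

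arm mean = p(U + D) + (1 − p)U = U + pD.

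For placebo this is U + 0.737D. One arm mean cannot separate U from D.

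**What the arm contrast contains.** If U and D are the same in both arms,

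placebo − palivizumab = (0.737 − p_pal) × D.

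**Cell sizes.** Placebo: 25 × 0.737 = 18.4 infected and 25 − 18.4 = 6.6 uninfected. For the whole trial, infected = 25 × (0.737 + p_pal). The palivizumab rate p_pal is an assumption, shown over its range from 0 to the placebo rate:

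| p_pal (assumed) | Arm contrast | Infected of 50 | Uninfected of 50 |
|---|---|---|---|
| 0% | 0.74D | 18.4 | 31.6 |
| 10% | 0.64D | 20.9 | 29.1 |
| 30% | 0.44D | 25.9 | 24.1 |
| 50% | 0.24D | 30.9 | 19.1 |
| 73.7% | 0 | 36.9 | 13.1 |

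The by-arm tables never isolate D, and how far they dilute it depends on a rate that is not known in advance. A pooled infected/uninfected table is feasible across the range. The within-arm split is thin: about 7 uninfected in placebo, and few or no infected in palivizumab if it works well.

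**Days measured.** Spirometry is optional on Days 1, 2, 3, 5, 6, 8, 9 and 10, which is 8 of the 12 days from Day 1 to Day 12. It is mandatory on Days 4, 7, 11 and 12, and again at Day 28. The number measured on an optional day may therefore differ from the number on a mandatory day, and SAP 5.6.9 gives no rule for this.

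**The case against.** The strongest reply is that little was promised. The note to the objectives in protocol 1.1.3.2 makes tertiary objectives optional, protocol 9.6.8 limits them to descriptive statistics, and the endpoint names no split by infection. Protocol 9.6.9 itself asks for spirometry by time and by treatment group as safety data, so the SAP tables carry out the protocol. In relation to infection could also be read loosely as change after challenge. All of this lowers the priority, and it means that the by-arm tables must stay. It does not close the gap: SAP 5.6.9 commits to six tables under Objective 11, and on the plan's own rate about a quarter of challenged placebo participants are not infected, so change after challenge is not change with infection.

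A second reply is that the safety set is in practice the challenged set, because protocol 1.1.6.2 expects no loss between dosing and inoculation. That is fair. The mixing of infected and uninfected remains.

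Three stronger readings are tempting, and the documents do not support them.

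- A reader might infer that the trial cannot answer the objective. Listings 16.2.13 to 16.2.15 give individual lung-function data and Listing 16.2.6.5 gives infection data, so a later summary is possible.
- A reader might infer that the symptom-triggered repeats allowed by protocol 8.9 enter the by-time tables. SAP 5.2.2.1 drops post-baseline retests, and SAP 5.2.5 generally leaves other unscheduled data unanalysed, in both cases unless the data review meeting decides otherwise.
- A reader might infer that spirometry on optional days selects the more symptomatic. The schedule says only that these measurements are optional or discretionary; the investigator could measure everyone or no one. Daily PEF is not affected at all.

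**Conclusion.** The mismatch stands, at minor priority. As planned, the lung-function tables compare arms and do not show the relation to infection that Objective 11 names. In placebo they mix about 74% infected with 26% uninfected. The arm contrast carries between 0 and 0.74 of any infection effect D, depending on the palivizumab infection rate.

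Those fractions assume that D and the change in the uninfected are the same in both arms. They show that dilution occurs, not that D is large; the documents give no value for D. The structural finding needs none of these assumptions. It rests on SAP 5.6, 5.6.9, 6 and 11.1 alone.

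The primary analysis, sample size and error rate are unaffected, and no further data are needed.

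**What to change.** Keep the by-arm safety-set tables that protocol 9.6.9 asks for. In SAP 5.6.9 and 11.1:

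1. Mark Tables 14.3.8.1 to 14.3.8.6 for the existing infected subgroup, using full variant 2 as in SAP 6. The first clause of variant 2 alone is set for the interim only (SAP 7.1), and using it here would give lung function a different infected group from every other subgroup output.
2. Add the uninfected among challenged participants as a descriptive comparator, by arm and pooled. The subgroup mark alone gives no comparator.
3. Label the contrast a non-randomised association. Infection arises after randomisation, and the pooled comparison mixes infection with treatment.
4. Show the number measured at each time. Base the infected/uninfected spirometry comparison on the mandatory days. PEF can use all days, and FOT only the days and participants measured.

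The cost is SAP wording and a few extra descriptive tables, with no new visits, samples or participants. The downside is imprecision: about 7 of 25 placebo participants would be uninfected, so within-arm figures should be read as description only. Because the second clause of variant 2 uses the culture result, and SAP 7.2 holds plaque assay data to the second database lock, these tables become final at that lock. The same edit can correct SAP 4.2.4, which files the lung-function endpoint under Objective 12.
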